#### 6.3.3. Vital Signs

Vital signs will be measured before blood collection for clinical laboratory assessments and PK analysis (where applicable) and will include measurements of systolic and diastolic blood pressure, pulse rate, and body temperature. Subjects should be in a seated position for at least 5 minutes before vital signs measurement.

#### 6.3.4. Clinical Safety Laboratory Assessments

All protocol-required laboratory assessments must be conducted in accordance with the Study Reference Manual or Laboratory Manual and the protocol Schedule of Assessments (Table 1). Laboratory requisition forms must be completed, and samples must be clearly labeled with the subject number, protocol number, site/center number, and visit date. Details for the preparation and shipment of samples will be provided by the laboratory and are detailed in the Study Reference Manual or the Laboratory Manual. Reference ranges for all safety parameters will be provided to the site by the laboratory responsible for the assessments.

A list of clinical laboratory tests and parameters is provided in Table 3.

All laboratory tests with values that are considered clinically significantly abnormal during participation in the study should be repeated until the values return to normal or baseline. If such values do not return to normal within a period judged reasonable by the Investigator, the etiology should be identified, if possible, and the Sponsor notified.

Clinical Study Flotocol - Ve

#### **Table 3:** Laboratory Tests

Diagnostic Screening Tests				
HBsAg     Hepatitis C antibody	• Pregnancy tests: (serum at Screening and urine at other visits; women of CBP only)			
• Anti-HBc	• FSH (as needed in women of non-CBP only)			
That Tibe	• At the Investigator's discretion, subjects may be screen alcohol and illicit drug use.			
Serum Chemistry				
• BUN	• Total carbon dioxide	• Uric acid		
• Creatinine	• Calcium	• Total bilirubin (+fractionated		
• Glucose (fasting not required)	• AST	if required)		
• Sodium	• ALT	• Total protein		
• Potassium	Alkaline phosphatase	• Albumin		
• Chloride				
Hematology				
Platelet count	• RBC Indices:	• WBC Differential:		
• RBC count	• MCV	• Neutrophils		
• WBC count (absolute)	• MCH	• Lymphocytes		
Reticulocyte count	• MCHC	• Monocytes		
Hemoglobin	Reticulocyte percentage	• Eosinophils		
Hematocrit		• Basophils		
Urinalysis				
Specific gravity	• Dipstick: pH, Glucose,			
• Microscopic examination (if blood or protein is abnormal Protein, Blood Ketones				
ATT 1				

ALT = alanine aminotransferase; Anti-HBc = anti-hepatitis B core antigen; AST = aspartate aminotransferase; BUN = blood urea nitrogen; CBP = child-bearing potential; FSH = follicle-stimulating hormone; HBsAg = hepatitis B surface antigen; MCH = mean corpuscular hemoglobin; MCHC = mean corpuscular hemoglobin concentration; MCV = mean corpuscular volume; RBC = red blood cell(s); WBC = white blood cell(s).

#### 6.3.5. Local Tolerability Scale

At each specified study visit, the Investigator (or qualified evaluator) will assess the presence and overall degree of irritation at the application sites, according to the LTS (an example of the LTS is provided in Appendix 8). The score will ideally represent an "average" across all application sites. To the fullest extent possible, the same Investigator (or designated evaluator) will perform all tolerability assessments for an individual subject throughout the study. If the subject is applying study treatment to "sensitive areas" (eg, genitals, face, neck, and skin folds), then the degree of irritation for these areas should also be assessed by the investigator.

Additionally, at each specified study visit, the participant will use a 5-point LTS to assess the presence and degree of burning/stinging and itching at the treatment areas. The score will ideally represent an "average" across all application sites.

## 6.4. Treatment of Study Drug Overdose

For this study, accidental or intentional oral ingestion of drug product will be considered an overdose. Ingestion of a 30-gram tube of tapinar of cream, 1% would result in an oral dose of 300 mg.

The Sponsor does not recommend specific treatment for an overdose; however, in the event of an overdose, the Investigator (or treating physician) should do the following:

- Contact Medical Monitor to discuss the event
- Closely monitor the subject for AEs/SAEs and laboratory abnormalities
- Provide general symptomatic treatment as necessary
- Document the quantity of the excess dose as well as the duration of the overdosing in the eCRF.
- If the Medical Monitor requests a plasma sample for PK analysis, then a blood sample for PK should be obtained within 2 days from the date of the last dose of study drug.

Decisions regarding dose interruptions or modifications following an overdose will be made by the Investigator in consultation with the Medical Monitor based on the clinical evaluation of the subject.

#### 6.5. Pharmacokinetics

A single blood sample for PK analysis of tapinar of cream, 1% will be collected at a subset of sites in a subset of subjects at timepoints indicated in the Schedule of Assessments (Table 1) and Section 7. The actual date and time of each blood sample collection will be recorded as well as the date and time of the last dose of study drug prior to sample collection. Collection, processing, storage, and shipping procedures are provided in the Laboratory Manual.

Concentrations of tapinarof will be determined in plasma samples using a validated bioanalytical method. Raw data will be archived at the bioanalytical site.

#### 7. TIMING OF PROCEDURES AND ASSESSMENTS

This section lists the procedures and assessment to be performed at scheduled timepoints during the study as outlined in the Schedule of Assessments (Table 1). Information on study procedures and assessment s is provided in Section 6.

- Any change in timing or any addition of a timepoint(s) for any planned study assessment must be documented in a "Note to File," which is approved by the relevant Sponsor study team member and then archived in the study Sponsor and site study files; this will NOT constitute a protocol amendment.
- The IRB/IEC will be informed of any safety issues that require alteration of the safety monitoring scheme or amendment of the Informed Consent Form (ICF).

NOTE: Assessments and procedures should be performed predose on clinic visit days.

## 7.1. Visit 1; Screening Period (Day -34 to Day -1)

After the subject has signed the Informed Consent Form (ICF), potential study subjects will undergo Screening procedures and assessments to confirm eligibility to participate in the study. Screening assessments will include the following:

- Demography recording
- Serum pregnancy test (females of child-bearing potential)
- Medical history recording
- ECG recording
- Brief physical examination (including weight, height, and body masss index [BMI])
- Vital signs measurements
- HADS assessment
- PGA score
- %BSA affected calculation; subject's scalp, palms, and soles should be excluded from the %BSA calculations used to determine patient's eligibility
- Blood sample collection for clinical laboratory tests (serum chemistry, hematology, diagnostic tests)
- Urinalysis
- AE recording (from the time the ICF is signed)
- Concomitant medication recording (from the time ICF is signed)

To determine subject eligibility at Screening, a single repeat of tests or procedures may be allowed at the discretion of the Investigator. The Medical Monitor should be consulted if needed.

## 7.2. Visit 2; Baseline (Day 1)

On Day 1, subjects will be reassessed to confirm continued eligibility to participate in the study. All subjects who continue to meet study eligibility criteria will be randomized to treatment.

The following additional procedures and assessments will be performed at the Baseline Visit:

- Urine pregnancy test (females of child-bearing potential)
- Changes to medical history will be recorded
- Brief physical examination
- Vital signs measurement
- Photography of a representative area of the subject's disease area (optional; at a subsection of study sites)

•

- PGA score
- %BSA affected calculation (performed before PASI); subject's scalp, palms, and soles should be excluded from the %BSA calculations used to confirm patient's eligibility
- PASI
- DLQI
- SF-36
- PSD
- Peak Pruritus-NRS
- AE recording
- Concomitant medication recording (from the time ICF is signed)
- Diary dispensed (subjects will be instructed in how and when to complete diary)
- Subject randomized to study treatment and registered in IVRS
- Study drug dispensed
- Instruction on how to apply study drug
- Study drug application under supervision

## 7.3. Double-Blind, Vehicle-Controlled Phase

Subjects will return to the study site at Weeks 2, 4, 8, and 12 and will be contacted by phone at Weeks 6 and 10 of the double-blind phase of the study.

#### 7.3.1. Visit 3; Week 2 (Day 15 $\pm$ 2 Days)

The following procedures and assessments will be performed at Visit 3:

- Vital signs
- PGA score
- %BSA affected calculation (performed before PASI)
- PASI
- LTS

- PSD
- Peak Pruritus-NRS
- AE recording
- Concomitant medication recording
- Collect and dispense subject diaries
- Review subject diaries for treatment compliance
- Collect and dispense study drug
- Review instructions on how to apply study drug
- Study drug application under supervision

#### 7.3.2. Visit 4; Week 4 (Day 29 $\pm$ 2 Days)

The following procedures and assessments will be performed at Visit 4:

- Urine pregnancy test (females of child-bearing potential)
- Brief physical examination
- Vital signs measurement
- Photography of a representative area of the subject's disease area (optional; at a subset of study sites)
- Blood sample collection for PK analysis (subset of sites and subjects)
- Blood sample collection for clinical laboratory tests
- PGA score
- %BSA affected calculation (performed before PASI)
- PASI
- LTS
- DLQI
- SF-36
- PSD
- Peak Pruritus-NRS
- AE recording
- Concomitant medication recording
- Collect and dispense subject diaries
- Review subject diaries for treatment compliance
- Collect and dispense study drug
- Review instructions on how to apply study drug
- Study drug application under supervision

#### 7.3.3. Visit 5; Week 8 (Day 57 $\pm$ 2 Days)

The following procedures and assessments will be performed at Visit 5:

• Urine pregnancy test (females of child-bearing potential)

- Brief physical examination
- Vital signs measurement
- Photography of a representative area of the subject's disease area (optional; at a subset of study sites only)
- PGA score
- %BSA affected calculation (performed before PASI)
- PASI
- LTS
- PSD
- Peak Pruritus-NRS
- AE recording
- Concomitant medication recording
- Collect and dispense subject diaries
- Review subject diaries for treatment compliance
- Collect and dispense study drug
- Review instructions on how to apply study drug
- Study drug application under supervision

#### 7.3.4. Visit 6; Week 12 (Day $85 \pm 2$ Days)

The following procedures and assessments will be performed at Visit 6:

- Urine pregnancy test (females of child-bearing potential)
- Brief physical examination
- Vital signs measurement
- Photography of a representative area of the subject's disease area (optional, at a subsection of study sites)
- Blood sample collection for PK analysis (subset of sites and subjects)
- Blood sample collection for clinical laboratory tests
- PGA score
- %BSA affected calculation (performed before PASI)
- PASI
- LTS
- DLQI
- SF-36
- PSD
- Peak Pruritus-NRS
- AE recording
- Concomitant medication recording

Collect subject diaries

- Review subject diaries for treatment compliance
- Collect study drug

#### 7.3.5. Phone Contact at Weeks 6 (Day 43 ±2 Days) and 10 (Day 71 ±2 Days)

Subjects will be contacted by phone at Weeks 6 and 10 to review study drug application instructions and to record AEs and concomitant medication use. Subjects should be reminded to complete their daily diary and bring it with them to the next clinic visit.

#### 7.4. Follow-Up Visit 7; Week 16 (Day 113 ±4 Days)

Subjects who do not enroll in the open-label long-term study will return to the study site at Week 16 to complete follow-up assessments as follows:

- Urine pregnancy test (females of child-bearing potential)
- Brief physical examination
- Vital signs measurement
- Blood sample collection for clinical laboratory tests
- Urinalysis
- PGA score
- %BSA affected calculation (performed before PASI)
- **PASI**
- LTS
- DLQI
- SF-36
- PSD
- Peak Pruritus-NRS
- AE recording
- Concomitant medication recording

#### 7.5. **Early Termination Visit**

Subjects who withdraw early from the study will be asked to return to the study site to complete Early Termination assessments as follows:

- Urine pregnancy test (females of child-bearing potential)
- Brief physical examination
- Vital signs measurement
- Blood sample collection for clinical laboratory tests
- Urinalysis
- PGA score
- %BSA affected calculation (performed before PASI)
- **PASI**
- LTS

- DLQI
- SF-36
- PSD
- Peak Pruritus-NRS
- AE recording
- Concomitant medication recording
- Collect subject diaries
- Review subject diaries for treatment compliance
- Collect study drug

## 7.6. End of Study

The end of study is defined as when the last active subject has completed the Week 16 Follow-up Visit 4 weeks after the end of treatment (if subject does not enroll in the separate long-term study) OR the last active subject has completed the 12 weeks of treatment in this study (if subject is eligible and enrolls in the separate long-term study).

#### 8. SAFETY MONITORING AND REPORTING

## 8.1. Adverse Events, Serious Adverse Events, and Adverse Events of Special Interest

The Investigator or site staff is responsible for detecting, documenting, and reporting events that meet the definition of an AE, SAE, or adverse events of special interest (AESIs). At each visit/contact, subjects should be questioned in a general way so as not to introduce bias in detecting AEs and/or SAEs. Open-ended and non-leading verbal questioning of the subject is the preferred method to inquire about AE occurrence.

Investigators are not obligated to actively seek AEs or SAEs in former study subjects. However, if the Investigator learns of any SAE, including a death, at any time after a subject has been discharged from the study, and he/she considers the event reasonably related to the study drug or study participation, the Investigator should promptly notify the Sponsor.

#### 8.1.1. Definition of Adverse Events

An AE is any untoward medical occurrence in a Subject temporally associated with the use of a medicinal product, whether considered causally related or not related to the medicinal product.

An AE can therefore be any unfavorable and unintended sign (including an abnormal laboratory finding), symptom, or disease (new or exacerbated) temporally associated with the use of a medicinal product.

Events meeting the definition of an AE include:

- Any abnormal laboratory test results (hematology, clinical chemistry) or other safety assessments (eg, vital signs measurements), including those that worsen from baseline, and felt to be clinically significant in the medical and scientific judgment of the Investigator
- Exacerbation of a chronic or intermittent pre-existing condition (eg, atopic dermatitis) including either an increase in frequency and/or intensity of the condition
  - For skin-related AEs, it should be noted whether or not the event is in the area of active application of study drug, and/or if spreading beyond the application site.
- New conditions detected or diagnosed after study drug administration even though it may have been present prior to the start of the study
- Signs, symptoms, or the clinical sequelae of a suspected interaction
- Signs, symptoms, or the clinical sequelae of a suspected overdose of either study drug or a concomitant medication (overdose per se will not be reported as an AE/SAE)
- "Lack of efficacy" or "failure of expected pharmacological action" per se will not be reported as an AE or SAE. Such instances will be captured in the efficacy assessments. However, the signs, symptoms, and/or clinical sequelae resulting from lack of efficacy will be reported as AE or SAE if they fulfill the definition of an AE or SAE.
- Symptomatic complaints at the site of local application (eg, burning/stinging, pruritus, and erythema)

Events that **do not** meet the definition of an AE include:

- Any clinically significant abnormal laboratory findings or other abnormal safety assessments that are associated with the underlying disease, unless judged by the Investigator to be more severe than expected for the subject's condition
- The disease/disorder being studied or expected progression, signs, or symptoms of the disease/disorder being studied, unless more severe than expected for the subject's condition
- Medical or surgical procedure (eg, endoscopy, appendectomy); the condition that leads to the procedure is an AE
- Situations where an untoward medical occurrence did not occur (social and/or convenience admission to a hospital)
- Anticipated day-to-day fluctuations of pre-existing disease(s) or condition(s) present or detected at the start of the study that do not worsen

#### 8.1.2. Definition of Serious Adverse Event

If an event is not an AE per Section 8.1.1, then it cannot be an SAE even if serious conditions are met (eg, hospitalization for signs/symptoms of the disease under study, death due to progression of disease, etc.).

An SAE is any untoward medical occurrence that, at any dose:

- Results in death
- Is life-threatening
  - The term "life threatening" refers to an event in which the subject was at risk of death at the time of the event. It does not refer to an event, which hypothetically might have caused death, if it were more severe.
- Requires hospitalization or prolongation of existing hospitalization
  - In general, signifies that the subject has been detained (usually involving at least an overnight stay) at the hospital or emergency ward for observation and/or treatment that would not have been appropriate in the physician's office or outpatient setting. Complications that occur during hospitalization are AEs. If a complication prolongs hospitalization or fulfills any other serious criteria, the event is serious. When in doubt as to whether "hospitalization" occurred or was necessary, the AE should be considered serious.
  - Hospitalization for elective treatment of a pre-existing condition that did not worsen from baseline is not considered an AE.
- Results in disability/incapacity: a substantial disruption of a person's ability to conduct normal life functions.
  - This definition is not intended to include experiences of relatively minor medical significance such as uncomplicated headache, nausea, vomiting, diarrhea, influenza, and accidental trauma (eg, sprained ankle) which may interfere or prevent everyday life functions but do not constitute a substantial disruption.
- Results in a congenital anomaly/birth defect
- Medical or scientific judgment should be exercised in deciding whether reporting is appropriate in other situations, such as important medical events that may not be immediately life-threatening or result in death or hospitalization but may jeopardize

the subject or may require medical or surgical intervention to prevent one of the other outcomes listed in the above definition. These should also be considered serious. Examples of such events are invasive or malignant cancers, intensive treatment in an emergency room or at home for allergic bronchospasm, blood dyscrasias, or convulsions that do not result in hospitalization, or development of drug dependency or drug abuse.

#### 8.1.3. Adverse Events of Special Interest

In prior clinical studies, the following AEs have been identified as AEs of particular clinical importance and will be reported as AESIs in this study; in each case study drug may be discontinued, based on Investigator judgment, and may be restarted when the event resolves:

- Contact dermatitis: the study site should collect location, duration, size, associated symptoms (itching, burning, pain), severity (mild, moderate, severe), and photograph the affected site (if possible). If the subject contacts the study site to report significant skin irritation at or near the site of study drug application between study visits, the subject should be brought in for an unscheduled visit, if possible.
- Folliculitis: the study site should collect the location, duration, size, associated symptoms (itching, burning, pain), severity (mild, moderate, severe), indicate whether pustular, and photograph the affected site (if possible).
- Headache: the study site should collect duration, severity (mild, moderate, severe), onset, and location (e.g., frontal, temporal, occipital, diffuse).

Additional AESIs may be identified by the Drug Safety Physician and if applicable by the Clinical Study Team Physician during the evaluation of safety data for the Clinical Study Report. For each AESI, a narrative may be written and included in the Clinical Study Report.

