### 4.6.1. Reasons for Withdrawal from the Study

Study drug will be discontinued for any of the following reasons:

- Subject has an AE that is considered to be related to study drug or procedures AND is severe enough to warrant treatment discontinuation, as determined by the Investigator (Section 8.1).
- Subject requires concurrent prohibited medication during the study. If, in the opinion of the Investigator and the study Medical Monitor, such medication will not interfere with the conduct or interpretation of the study or compromise the safety of the subject, then the subject may continue to receive study drug. If the subject is discontinued from study drug, they may remain in the study for safety assessments as needed, at the discretion of the Investigator and Medical Monitor.
- Pregnancy
- Any Grade 3 or 4 AE considered causally related to study drug (Section 8.2.2)

Study drug may be discontinued for any of the following reasons:

• Subject noncompliance

- Investigator noncompliance
- Discontinuation of the study at the request of the Sponsor, regulatory agency, or an Institutional Review Board (IRB)/Independent Ethics Committee (IEC).

If a subject meets a withdrawal criterion during treatment, an Early Termination visit will be required (Section 7.5).

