#### 8.2. Classification of Adverse Events

#### 8.2.1. Assigning Severity Rating for Adverse Events

#### 8.2.1.1. Criteria for Determining Averse Event Severity

The Investigator will make an assessment of the severity of each AE and SAE according to the National Cancer Institute Common Terminology Criteria for Adverse Events (CTCAE), v. 5.0, 2017. For terms not specified with the CTCAE, the criteria in Table 4 should be used to determine the grade severity.

Table 4: Criteria for Determining the Grade/Severity of Adverse Event Terms Not Specified by the National Cancer Institute CTCAE

Grade	Criteria	
1	Mild; asymptomatic or mild symptoms, clinical or diagnostic observations only; intervention not indicated	
2	Moderate; minimal, local, or noninvasive intervention indicated; limiting age-appropriate instrumental activities of daily living a	
3	Severe or medically significant but not immediately life-threatening; hospitalization or prolongation of hospitalization indicated; disabling; limiting self-care activities of daily living b	
4	Life threatening consequences; urgent intervention indicated	
5	Death related to adverse event	

CTCAE = Common Terminology Criteria for Adverse Events.

- a Instrumental activities of daily living refer to preparing meals, shopping for groceries or clothes, using the telephone, managing money, etc.
- b Self-care activities of daily living refer to bathing, dressing and undressing, feeding self, using the toilet, taking medications, and not bedridden.

Adverse event severity should be recorded in the appropriate section of the adverse event case report form and in the subject's source documents.

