#### 8.2.1.2. Toxicity Management Criteria

#### 8.2.1.2.1. Grade 1 or Grade 2 Adverse Event

Subjects who develop a Grade 1 or Grade 2 AE may continue investigational product at the discretion of the Investigator. Subjects who choose to withdraw from study due to a Grade 1 or 2 AE should have study withdrawal/follow-up evaluations completed.

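### Protocol 8.1.3 makes stopping optional and allows restart for contact dermatitis, folliculitis and headache at any grade, which conflicts with the stopping rules in 4.6.1 and 8.2.1.2

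*Protocol*

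**What the plan says.** Protocol Section 8.1.3 names contact dermatitis, folliculitis and headache as adverse events of special interest and says that "in each case study drug may be discontinued, based on Investigator judgment, and may be restarted when the event resolves". Resolution of the event is the only condition on restart. Severe events are within scope, since severity is recorded up to severe for all three. The headache entry, for example, reads "Headache: the study site should collect duration, severity (mild, moderate, severe), onset, and location".

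The general stopping rules stand elsewhere in the protocol:

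- **Section 4.6.1** opens a list with "Study drug will be discontinued for any of the following reasons". One entry is "Any Grade 3 or 4 AE considered causally related to study drug". It adds: "If a subject meets a withdrawal criterion during treatment, an Early Termination visit will be required".
- **Section 8.2.1.1** applies grading to all events: "The Investigator will make an assessment of the severity of each AE and SAE".
- **Section 8.2.1.2.1** leaves low grades to judgment: "Subjects who develop a Grade 1 or Grade 2 AE may continue investigational product at the discretion of the Investigator".
- **Section 8.2.1.2.2** calls for stopping when a Grade 3 event is considered related or possibly related. Otherwise dosing may go on only if there is compelling evidence that the product was not the cause, and after the Medical Monitor has been consulted.
- **Section 8.2.1.2.3** calls for a permanent stop after a Grade 4 event, with no reference to causality.

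Section 8.1.3 cites none of these, and none of them makes an exception for the three events. SAP Section 12.9.1 summarises grade, causality and action taken with study drug for these events but sets no stopping rule.

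**The concern.** Two parts of one protocol give a site different instructions for the same subject. Someone who turns to the section on the named event finds that stopping is a matter of judgment and that the drug may be restarted. Someone who turns to the withdrawal criteria finds that a related Grade 3 event requires a stop and an Early Termination visit.

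These are events that sites can expect to meet. Section 1.3.1.1 gives folliculitis and contact dermatitis as the most frequent dermatologic events in the psoriasis dose-ranging study, and Section 1.3.1.2 places headache among the most frequent nondermatological ones. Section 1.3.1.1 also warns that a pronounced skin reaction may spread beyond the application site, so re-exposure after a severe related reaction is a genuine safety question. The trial runs at about 50 to 60 sites (Section 4.1) without an independent data monitoring committee (Section 8.6), so much depends on site-level rules being clear.

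**Working it through.** No arithmetic applies. The check sets 8.1.3 beside the general rules, grade by grade.

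- **Grades 1 and 2.** Both 8.1.3 and 8.2.1.2.1 leave continuation to the Investigator. There is no conflict.
- **Grade 3, considered related.** Under 8.1.3 stopping is optional. Under 4.6.1 it is required, and under 8.2.1.2.2 it should happen. This is a direct conflict on stopping. On restart, the conflict is with 4.6.1. That section requires an Early Termination visit, which Section 7.5 describes for people leaving the study: "Subjects who withdraw early from the study will be asked to return to the study site to complete Early Termination assessments". Study drug is collected at that visit, and no route back to dosing is given.
- **Grade 3, possibly related.** 8.2.1.2.2 again calls for a stop, and 8.1.3 leaves it optional.
- **Grade 3, not considered related.** 8.2.1.2.2 allows dosing to continue on two conditions, compelling evidence and discussion with the Medical Monitor. 8.1.3 mentions neither, so it is looser.
- **Grade 4, any causality.** 8.2.1.2.3 makes the stop permanent, and 4.6.1 also applies when the event is related. 8.1.3 allows both continuation and restart, so it conflicts on both. For terms outside the CTCAE, Table 4 defines Grade 4 as life-threatening, while 8.1.3 records severity only up to severe. Such cases should be rare for these three events.

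The conflict that a site could realistically meet is therefore the Grade 3 event considered related.

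Three other passages bear on the point without settling it. Section 1.3.1.1 allows treatment to be interrupted for skin reactions but gives no grade limit. The first stop reason in 4.6.1 points to Section 8.1, the parent of 8.1.3, but only for stops that the Investigator decides on, and it does not say which text governs. Section 8.2.1.2.4 has the Medical Monitor notified of severe signs that put a subject at risk, which is notification and not a stop.

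**The case against.** The best defence is that this is a missing cross-reference and not a contradiction. Section 8.1.3 is permissive, and the other rules cover all events of the stated grade. A site can comply with all of them by stopping where 4.6.1 or 8.2.1.2 says so and using judgment elsewhere. Section 8.1.3 claims no exemption, and Section 6 bars waivers and exemptions except for immediate safety concerns.

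That reading is plausible, and it is probably what the sponsor meant. But no passage states it. A clause that names specific events and covers each case can as naturally be read as governing those events. A reader should not need to infer precedence between safety rules.

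Part of the defence limits the point. A reader might infer that 8.2.1.2.2 itself forbids restart after any related Grade 3 event. It does not: it speaks separately of Grade 3 events that require permanent discontinuation, which implies that some do not. The restart conflict for Grade 3 rests on 4.6.1 and its Early Termination visit, and 4.6.1 does not use the word permanent. A reader might also infer that the three events have no stopping rule at all. They have one, because the general rules reach them on their face. The fault is that 8.1.3 is not reconciled with those rules.

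**Conclusion.** Section 8.1.3 is wrong as written: it is inconsistent with the protocol's own safety rules. A site that follows it literally could keep dosing, or rechallenge, a subject whom 4.6.1 requires to stop.

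The severity is low. The documents give no rate of these events by grade and causality. Section 1.1.1 reports that most treatment-emergent events in the Phase 2b studies were mild or moderate, so few subjects are likely to be affected. The comparison by grade shows where the texts disagree, not how often that would matter.

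A reader might go on to infer a threat to the efficacy conclusion. The documents do not support that: the point concerns subject safety and uniform conduct across sites, and it does not touch the primary result. The conclusion assumes only that Grade 3 events of these types can occur and be judged related, which the protocol's own grading and severity fields allow for.

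**What to change.** In Section 8.1.3, delete the words *in each case* and open the clause with: *subject to the mandatory discontinuation rules in Sections 4.6.1 and 8.2.1.2, which take precedence,*. The rest of the clause, on Investigator judgment and restart after resolution, stays as it is. This keeps the flexibility for manageable events and brings in the Grade 3 conditions of 8.2.1.2.2 by reference.

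Nothing further is needed. Section 4.6.1 should stay unchanged. Adding every Grade 4 event to its list would make an Early Termination visit compulsory for unrelated Grade 4 events, where 8.2.1.2.3 only encourages withdrawal evaluations.

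The cost is one clause, submitted as a protocol modification under Section 11.2.1, and a notice to sites. Endpoints, sample size and the SAP do not change.
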